The mean change from baseline at weeks 12, 28, and 52 weeks will be computed for each treatment group for the following endpoints. A paired t-test will be used to assess within treatment effect. Between treatment difference will be assessed using MMRM using baseline subscore as a covariate and treatment group, visit, the interaction of treatment and visit, and stratification factors as fixed effects. The same strategy as that used in MMRM for Hb will be used to choose variance covariance structure. Non-inferiority of roxadustat vs. Epoetin will be tested. The non-inferiority margin is fixed as a difference of 2 points. Mean change in these endpoints at above-mentioned time points will be analyzed and compared between the 2 treatment groups using MMRM using the baseline value as a covariate, treatment group, visit, the interaction of treatment and visit, adjusting for the stratification factors. The same strategy as that used in MMRM for Hb will be used to choose variance covariance structure. Other than below endpoints for exploratory analyses, other QoL variables may be performed.

HRQoL benefit will be assessed using SF-36 vitality and physical functioning subscales

- **Change from Baseline in SF-36 Vitality (VT) Sub-Score**

The change from baseline in SF-36 VT sub-score to the average VT sub-score will be analyzed using MMRM with baseline VT subscore as a covariate and treatment group, visit, the interaction of treatment and visit, and stratification factors as fixed effects. The same strategy as that used in MMRM for Hb will be used to choose variance covariance structure. Data up to visit of Week 52 will be included in the analyses. The estimates for the difference of change from baseline in SF-36 VT for Week 12 to 28 between two treatment groups will be generated from an estimate statement. Non-inferiority of roxadustat vs. Epoetin will be tested.

- **Change from Baseline in SF-36 Physical Functioning (PF) Sub-Score**

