16.5 Appendix 5 Data Handling Conventions

16.5.1 Visit Time Windows

The table below presents the visits assigned for efficacy and safety analyses corresponding to the range of treatment days (window) during which an actual visit may have occurred.

Table 11. Visit Time Windows

Derived Visit	Scheduled Visit Day ^a	Window
Baseline, Week 0	Day 1	Days ≤ 1
Week 1	Day 7*(Week #)+1	Days [Day 2, 10]
Week 2	Day 7*(Week #)+1	Days [Scheduled Day ± 3 Scheduled Day ± 6]
Weeks 4 prior to 24	Day 7*(Week #)+1	Days [Scheduled Day ± 7 , Scheduled Day ± 6]
Week 24	Day 7*(Week #)+1	Days [Scheduled Day ± 7 Scheduled Day ± 13]
\geq Week 28	Day 7*(Week #)+1	Days [Scheduled Day ± 14 , Scheduled Day ± 13]
ET	Earlier Termination, match to a closest scheduled visit in protocol if patient had not been off drug for more than 7 days.	
EoT	Last assessment between Day 2 and EOT visit day, match to a closest scheduled visit in protocol if patient had not been off drug for more than 7 days.	
EoS (FU-4Wk)	Final visit for the Study 15 – 31 days after the last dose (excluding long term follow-up for early termination).	

^a: Relative to the first study medication date. For example, Day 1 = the first dose date of study medication.

Table 12: Analysis Visit Windows for QoL

CRF Visit	Target Day ^a	Analysis Visit Windows Actual Assessment Day	Analysis Visit
Day 1	Day 1	Day 1	Baseline
Week 12	Day 7 * (Week #) + 1	Target day -14, Target Day + 27	Week 12
Week 28	Day 7 * (Week #) + 1	Target Day – 28, Target Day +83	Week 28
Week 52	Day 7 * (Week #) + 1	Target Day – 84, Target Day + 83	Week 52
EOT Visit		Last assessment between Day 2 and EOT visit day, remapped to the closest next scheduled visit for HRQoL collection.	Week 12, 28, 52 and > 1 year

^a: Relative to Day 1 (first dose date of study medication)

Table 13. Analysis Visit Windows for Lipid Panel

Derived Visit	Scheduled Visit Day ^a	Window
Baseline, Week 0	Day 1	Day 1
Week 4	Day 7*(Week #)+1	[Day 2, Day +42]
Week 8	Day 7*(Week #)+1	[Scheduled Day-14, Scheduled Day +13]
Weeks 12	Day 7*(Week #)+1	[Scheduled Day -14, Scheduled Day +27]
Week 20, 28	Day 7*(Week #)+1	[Scheduled Day -28, Scheduled Day +27]
Weeks 36	Day 7*(Week #)+1	[Scheduled Day -28, Scheduled Day +41]
Week 48 to xx	Day 7*(Week #)+1	[Scheduled Day -42, Scheduled Day +41]
Week xx	.	Last assessment between Day 2 and EOT visit day, match to a closest scheduled visit in protocol if patient had not been off drug for more than 7 days

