FU-4Wk		Final visit in the Study 15 – 31 days after Last Dose.

^a: Relative to Day 1 (first dose date of study medication)

Visit Day is calculated by (visit date – first dose date of study medication + 1). If a subject has ≥ 2 actual visits within the same window, the last visit with non-missing value will be used for analysis.

Repeated or Unscheduled Assessments of Safety Parameters

If a subject has repeated assessments prior to the start of study medication, then the results from the final assessment made prior to the start of study medication will be used as baseline. If end of study assessments are repeated or unscheduled, the last post-baseline assessment will be used as the end of study assessment for generating summary statistics. However, all post-baseline assessments will be used for PCS value determination and all assessments will be presented in the data listings.

Missing Date of Study Medication

When the last date of study medication during the study treatment phase is missing, all efforts should be made to obtain the date from the investigator. If it is still missing after all efforts, then the last visit date during the Treatment Period will be used in the calculation of treatment duration.

Missing Severity Assessment for Adverse Events

If severity is missing for an AE started prior to the first study medication, then a severity of “Mild” will be assigned. If the severity is missing for an AE started on or after the first study medication dosing, then a severity of “Severe” will be assigned. The imputed values for severity assessment will be used for incidence summary, while the actual missing values will be presented in data listings.

Missing Relationship to Study Drug for Adverse Events

If the relationship to the study medication is missing for an AE started after baseline, a causality of “Related” will be assigned. The imputed values for relationship to study medication will be used for incidence summary, while the actual values will be presented in data listings.

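### The SAP's EOT row for HRQoL, read as the next visit, files forms up to 16 or 24 weeks ahead of their completion, against the table's own windows

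*SAP*

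**What the plan says.** SAP 16.5.1, Table 12, is the visit-window table for quality of life. Its windows around the target day are "Target day -14, Target Day + 27" for Week 12, "Target Day – 28, Target Day +83" for Week 28 and "Target Day – 84, Target Day + 83" for Week 52. A further row, for the EOT visit, reads "Last assessment between Day 2 and EOT visit day, remapped to the closest next scheduled visit for HRQoL collection" and can feed "Week 12, 28, 52 and > 1 year".

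The EOT rows of Table 11 (general visits) and Table 13 (lipids) are worded differently: "match to a closest scheduled visit in protocol if patient had not been off drug for more than 7 days". For several visits in one window, the section says "the last visit with non-missing value will be used for analysis".

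SAP 11.3.7 analyses SF-36 Vitality and Physical Functioning by MMRM with data up to Week 52, and takes the treatment difference over Weeks 12 to 28. It adds: "The non-inferiority margin is fixed as a difference of 2 points". SAP 4.3 also asks for the average over Weeks 28 to 52.

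In the protocol, HRQoL is scheduled at Day 1, Weeks 12, 28 and 52, and EOT/ET (7.1.2 and Appendix 3). Subjects who stop study drug have their EOT assessments at withdrawal or as soon as possible afterwards (7.1.2.5). A Week 28 or Week 52 questionnaire due within 2 weeks of the planned EOT visit may be held over to that visit (7.1.2.4).

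**The concern.** An early-termination questionnaire can fall on any study day. The same is true of some subjects who do not stop early, because protocol 4.1 allows treatment to be shortened for those enrolled under Amendments 1 and 2, with all active subjects ending together. The rule that places these forms therefore matters.

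The Table 12 EOT row looks forward and is unbounded. A form can lie inside one visit's window and still be filed under the following visit. The MMRM would then take a score from about three months as an observed Week 28 score, which is carry-forward by date assignment. An MMRM does not need later visits filled. If the arms diverge over time, moving earlier scores to later visits shrinks the estimated difference, and in a non-inferiority comparison a smaller difference is easier to pass.

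**Working it through.** **Inputs.** Table 12 gives the target day as 7 x week + 1:
- Week 12: 7 x 12 + 1 = 85
- Week 28: 7 x 28 + 1 = 197
- Week 52: 7 x 52 + 1 = 365

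**Windows.**
- Week 12: 85 - 14 = 71 to 85 + 27 = 112
- Week 28: 197 - 28 = 169 to 197 + 83 = 280
- Week 52: 365 - 84 = 281 to 365 + 83 = 448

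**Window against EOT row.** Here the EOT row is read as the next target day on or after the assessment. Forward shift = target day minus assessment day.

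| Assessment day | By window | By EOT row | Forward shift (days) |
|---|---|---|---|
| 2-70 | none | Week 12 | 15-83 |
| 71-85 | Week 12 | Week 12 | 0-14 |
| 86-112 | Week 12 | Week 28 | 85-111 |
| 113-168 | none | Week 28 | 29-84 |
| 169-197 | Week 28 | Week 28 | 0-28 |
| 198-280 | Week 28 | Week 52 | 85-167 |
| 281-365 | Week 52 | Week 52 | 0-84 |
| 366-448 | Week 52 | > 1 year | - |

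The largest shifts in the two conflicting bands are 111 / 7 = 15.9 weeks and 167 / 7 = 23.9 weeks. Of the 364 days from Day 2 to Day 365:
- the two rules disagree on 27 + 83 = 110 (30%);
- they agree on 15 + 29 + 85 = 129 (35%);
- 69 + 56 = 125 (34%) have no window.

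These are counts of possible days, not of subjects.

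**Held-over Week 28 form.** Counting from the target day, a Week 28 form postponed by up to 2 weeks falls on Days 198-211. The EOT row files it as Week 52, which is 365 - 211 = 154 to 365 - 198 = 167 days early.

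**Where each shift lands.** Forms from Days 86-112 filed as Week 28 enter the Weeks 12-28 contrast directly. Forms from Days 198-280 filed as Week 52 enter the Week 52 comparison and the Weeks 28-52 average. They touch the Weeks 12-28 contrast only by leaving Week 28 and through the model's covariance.

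**Size, by assumption only.** The documents give no HRQoL standard deviation and no discontinuation rate. Suppose the arms do not differ at Week 12 and differ by g at Week 28, and a share f of Week 28 scores is carried from before they diverge. The Week 28 difference falls from g to g(1 - f), a loss of f x g. With Weeks 12 and 28 weighted equally, the contrast falls from g/2 to g(1 - f)/2, a loss of f x g / 2. For f = 5-20% and g = 2-4 points:
- loss at Week 28: 0.05 x 2 = 0.1 to 0.20 x 4 = 0.8 points;
- loss in the Weeks 12-28 contrast: 0.05 to 0.4 points.

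**The case against.** Table 12 is keyed by CRF visit, so the window rows may be meant for scheduled forms and the EOT row for EOT forms only. On that reading there is no collision, and forms from Days 2-70 or 113-168, which will nearly all be EOT forms, do have a place. This narrows the point but does not remove it: an early-termination form from Day 86 is still analysed as a Week 28 score. The row also speaks of the last assessment up to EOT, which could be a scheduled form. A reader might infer that ordinary Week 12 forms are routinely moved to Week 28. That is a literal but strained use of a row labelled EOT, and the text does not settle it.

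The wording also contains *closest*. Read that way, Days 86-140 go to Week 12 and Days 198-280 to Week 28 (Days 141 and 281 are ties), and the conflict with the windows disappears. The missing off-drug limit remains.

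The SAP leaves SF-36 out of its secondary list (4.2) and out of the Table 6 sequence, and 11.3.7 introduces these endpoints as exploratory. That stands: no confirmatory claim in the SAP rests on this rule. The protocol, however, still has both subscores as fixed-sequence secondary endpoints (9.4.3.2).

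Last, early-termination scores are not necessarily close to baseline. They are taken at withdrawal, sometimes for an adverse event or lack of efficacy, and may be poor. Keeping them could count against the arm with worse discontinuations, while dropping them makes the MMRM lean on missing-at-random. That also stands.

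**Conclusion.** The point holds as a defect in a stated rule. Read as *next*, the Table 12 EOT row places forms from Days 86-112 at Week 28 and forms from Days 198-280 at Week 52, up to 111 and 167 days early. It contradicts the table's own windows and departs from Tables 11 and 13 without explanation. The wording is ambiguous and no precedence is given, which in an open-label trial should be closed before analysis.

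Three stronger conclusions are not supported. A reader might infer that the rule biases the result towards non-inferiority; that requires the arms to diverge over time and early scores to show less difference, and the documents show neither. A reader might set a diluted Week 28 difference against the 2-point margin; the contrast averages Weeks 12 and 28, so under the equal-weight illustration the effect is halved, and its inputs are assumed. A reader might place the 24-week shift inside the Weeks 12-28 contrast; those scores are filed at Week 52.

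Given the exploratory status in the SAP, this should be corrected but does not threaten the primary analysis.

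**What to change.** Replace the Table 12 EOT row with one rule for every HRQoL form, including EOT and ET forms: assign by actual assessment day to contiguous windows. For example, Week 12 = Days 71-140, Week 28 = Days 141-280 and Week 52 = Days 281-448. Forward shifts are then at most 85 - 71 = 14, 197 - 141 = 56 and 365 - 281 = 84 days.

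- Apply the 7-day off-drug limit of Tables 11 and 13.
- Do not remap forms from before Day 71 to Week 12.
- Assign each form to one visit only, and say which form is used when a scheduled form and an ET form share a window, since the present last-value rule would choose the later one.
- Leave later visits missing for the MMRM.

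The cost is one table edit and one derivation to reprogram, slightly fewer Week 28 and Week 52 scores, and reliance on missing-at-random. The current remapping can be kept as a sensitivity analysis, which would also show how much the choice matters.

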16.5.2 Missing Date Imputation for Adverse Events

- **Incomplete Start Date**

The following imputation rules only apply to the case where the start date is incomplete (i.e., partial missing) for adverse events.

Missing day and month

- If the year is same as the year of first day on study medication, then the day and month of the start date of study medication will be assigned to the missing fields.
- If the year is not the same as the year of first day on study medication, then January 1 will be assigned to the missing fields.

Missing month only

Treat day as missing and replace both month and day according to the above procedure.

Missing day only

If the month and year are same as the year and month of first day on study medication, then the start date of study medication will be assigned to the missing day.

If the month and year are not the same as the year and month of first day on study medication, then the first day of the month will be assigned to the missing day.

If the stop date is complete and the imputed start date as above is after the stop date, the start date will be imputed by the stop date.

- **Incomplete Stop Date**

If needed, the following imputation rules apply to the case where the end date is incomplete (i.e., partially missing) for adverse events. Other partial end date will not be imputed.

Missing day and month, or Missing month only

December 31 will be assigned to the missing fields.

Missing day only

The last day of the month will be assigned to the missing day.

16.5.3 Missing Date Imputation for Prior or Concomitant Medications

For prior or concomitant medications, including rescue medications, incomplete (i.e., partial missing) start date and/or stop date will be imputed. When the start date and the stop date are both incomplete for a subject, impute the start date first.

- **Incomplete Start Date**

The following rules will be applied to impute the missing numerical fields. If the stop date is complete and the imputed start date is after the stop date, then the start date will be imputed using the stop date.

Missing day and month

If the year of the incomplete start date is the same as the year of the first dose date of study medication, then the day and month of the first dose date will be assigned to the missing fields.

If the year of the incomplete start date is prior to the year of the first dose date of study medication, then December 31 will be assigned to the missing fields.

If the year of the incomplete start date is after the year of the first dose date of study medication, then January 1 will be assigned to the missing fields.

Missing month only

Treat day as missing and replace both month and day according to the above procedure.

Missing day only

If the month and year of the incomplete start date are the same as the month and year of the first dose date of study medication, then the day of the first dose date will be assigned to the missing day.

If either the year is before the year of the first dose date of study medication or if both years are the same but the month is before the month of the first dose date of study medication, then the last day of the month will be assigned to the missing day.

If either the year is after the year of the first dose date of study medication or if both years are the same but the month is after the month of the first dose date of study medication, then the first day of the month will be assigned to the missing day.

Incomplete Stop Date

The following rules will be applied to impute the missing numerical fields. If the last dose date of study medication is missing, replace it with the last visit date. If the imputed stop date is before the start date (imputed or non-imputed start date), then the imputed stop date will be equal to the start date.

Missing day and month

If the year of the incomplete stop date is the same as the year of the last dose date of study medication, then the day and month of the last dose date will be assigned to the missing fields.

If the year of the incomplete stop date is prior to the year of the last dose date of study medication, then December 31 will be assigned to the missing fields.

If the year of the incomplete stop date is after the year of the last dose date of study medication, then January 1 will be assigned to the missing fields.

Missing month only

Treat day as missing and replace both month and day according to the above procedure.

Missing day only

If the month and year of the incomplete stop date are the same as the month and year of the last dose date of study medication, then the day of the last dose date will be assigned to the missing day.

If either the year is before the year of the last dose date of study medication or if both years are the same but the month is before the month of the last dose date of study medication, then the last day of the month will be assigned to the missing day.

If either the year is after the year of the last dose date of study medication or if both years are the same but the month is after the month of the last dose date of study medication, then the first day of the month will be assigned to the missing day.

16.5.4 Missing Date Imputation for last dose date

Imputed last dose date = earliest date of (last drug dispense date + number of days of drug dispensed, date of death, date of EOT/EOS visit, and other dates as appropriate).

16.5.5 Character Values of Clinical Laboratory Parameters

If the reported value of a clinical laboratory parameter cannot be used in a statistical summary table due to, for example, that a character string is reported for a parameter of the numerical type, coded value needs to be appropriately determined and used in the statistical analyses. However, the actual values as reported in the database will be presented in data listings.

Example for Coding of Special Character Values for Clinical Laboratory Parameters

Lab Test	Possible Lab Results (in SI unit)	Coded Value for Analysis
Chemistry: ALT	< 5	5
Chemistry: AST	< 5	5
Chemistry: Bilirubin, Total	< 2	2
Urinalysis: Glucose	= OR > 55, >= 55, > 0	Positive
	<= 0, Negative	Negative
Urinalysis: Ketones	= OR > 8.0, >=8.0, > 0	Positive
	<= 0, Negative	Negative
Urinalysis: pH	> 8.0, >= 8.0	8.0
	>= 8.5,	8.5
Urinalysis: Protein	= OR > 3.0, >=3.0, > 0	Positive
	<= 0	Negative

16.6 Appendix 6 Ranges of Potentially Clinically Significant Lab Values

Parameter	SI Unit	Lower Limit	Higher Limit
CHEMISTRY			
Alanine Aminotransferase (ALT)	U/L		≥3 * ULN
Alkaline Phosphatase	U/L		≥3 * ULN
Aspartate Aminotransferase (AST)	U/L		≥3 * ULN
GGT	U/L		≥3 * ULN
Calcium	mmol/L	<0.8*LLN	>1.2 * ULN
Creatinine	μmol/L		> 1.5x Day 1
Potassium	μmol/L	<0.75*LLN	>1.2 * UNL
Sodium	mmol/L	<0.9*LNL	>1.1 * UNL
Total Bilirubin	μmol/L		>1.5 * UNL
Total Protein	μmol/L	<0.9*LNL	>1.1 * UNL
Urea (BUN)	mmol/L		>1.5X Day 1
HEMATOLOGY			
Neutrophils	10 ⁹ /L	≤1	
Platelet Count	10 ⁹ /L	≤ 100	≥700
White Blood Cell Count	10 ⁹ /L	≤2.5	≥15
LLN: Lower limit of normal, value provided by the laboratory ULN: Upper limit of normal, value provided by the laboratory			

16.7 Appendix 7 Justification of the Non-Inferiority Margin

Non-Inferiority (NI) Clinical Trials states that “the NI trial concept depends on how much is known about the size of the treatment effect the active comparator will have in the NI study compared to no treatment” and this effect “must be assumed, based on an analysis of past studies of the control”.

Pursuant to this, we sought out studies that compared ESA therapies currently approved for use in the United States to placebo (or no therapy) in the treatment of anemia.

Criteria to be considered relevant to estimate the potential treatment effect included:

- 1- Randomized trial design
- 2- Prospective follow up
- 3- Treatment groups which included epoetin-alfa (or other recombinant erythropoietin derivatives) and either placebo or no treatment
- 4- Inclusion of treatment naïve adult patients with ESRD related anemia.
- 5- Post randomization monitoring of hemoglobin following randomization

Studies were identified through a search of the bibliographies of peer-reviewed meta-analyses examining the effect of ESAs on outcomes.

1. Palmer et al. Meta-analysis: Erythropoiesis-Stimulating Agents in Patients with Chronic Kidney Disease. *Ann Intern Med.* 2010;153:23-33.
2. Phrommintikul A et al. "Mortality and target haemoglobin concentrations in anaemic patients with chronic kidney disease treated with erythropoietin: a meta-analysis." *The lancet* 369.9559 (2007): 381-388.
3. Koulouridis, Ioannis, et al. "Dose of erythropoiesis-stimulating agents and adverse outcomes in CKD: a metaregression analysis." *American Journal of Kidney Diseases* 61.1 (2013): 44-56.

Identification of all appropriate trials was confirmed through a literature search (www.pubmed.gov) using combinations of the terms “ESA”, “epoetin”, “CKD”, “ESRD”, “placebo”, and “anemia”.

[figure not shown]
The approach taken for this NI margin is the fixed margin method described in the U.S. Food and Drug Administration’s 2010 guidance “Non-Inferiority Clinical Trials.” In this guidance, the fixed margin approach is summarized as follows:

“Briefly, in the fixed margin method, the margin M_1 is based upon estimates of the effect of the active comparator in previously conducted studies, making any needed adjustments for changes in trial circumstances. The NI margin is then pre-specified and it is usually chosen as a margin smaller than M_1 (i.e., M_2), because it is usually felt that for an important endpoint a reasonable fraction of the effect of the control should be preserved.

The NI study is successful if the results of the NI study rule out inferiority of the test drug to the control by the NI margin or more. It is referred to as a fixed margin analysis because the past studies comparing the drug with placebo are used to derive a single fixed value for M_1 , even though this value is based on results of placebo-controlled trials (one or multiple trials versus placebo) that have a point estimate and confidence interval for the comparison with placebo. The value typically chosen is the lower bound of the 95% CI (although this is potentially flexible) of a placebo-controlled trial or meta-analysis of trials. This value becomes the margin M_1 , after any adjustments needed for concerns about constancy.

The fixed margin M_1 , or M_2 if that is chosen as the NI margin, is then used as the value to be excluded for C-T in the NI study by ensuring that the upper bound of the 95% CI for C-T is $<M_1$ (or M_2). This 95% lower bound is, in one sense, a conservative estimate of the effect size shown in the historical experience. It is recognized, however, that although we use it as a “fixed” value, it is in fact a random variable, which cannot invariably be assumed to represent the active control effect in the NI study.” This approach is shown schematically in Figure 1.

Figure 1 Active Control – Test Drug differences (Point estimate, 95% CI)

1. C-T point estimate = 0 and upper bound of 95% CI $< M_2$, indicating test drug is effective (NI demonstrated).
2. Point estimate of C-T favors C and upper bound of 95% CI $< M_1$ but $> M_2$, indicating effect > 0 but unacceptable loss of the control effect.
3. Point estimate of C-T is zero and upper bound of 95% CI $< M_1$ but it is slightly greater than M_2 . Judgment could lead to conclusion of effectiveness.
4. C-T point estimate favors C and upper bound of 95% CI $> M_1$, indicating there is no evidence of effectiveness for test drug.”

Table 14 below displays the mean change in hemoglobin for recombinant human (EPO) based on 3 publications, [Canadian et al, 1990], [Bennett et al, 1991] and [Nissenson et al, 1995]. The 3 studies are all randomized, double-blinded, randomized, placebo controlled study to evaluate the effect EOP (epoetin alfa or beta) in anemia patient with ESRD with PD or HD.

Using the data in Table 14 below, the weighted mean of the point estimate of treatment effect in mean change from baseline for EPO (mean change in hemoglobin or hemoglobin equivalence in EPO group – mean change in placebo group) was calculated, along with its 95% confidence interval.

Table 14. Historical studies with mean change and SD in hematocrit or hemoglobin available in ESRD: EPO versus Placebo

[figure not shown]
Nissenson et al, 1995 (Erythropoietin in Peritoneal Dialysis)	Endpoint	EPO Mean (SD)	Placebo Mean (SD)	EPO-Placebo Mean (Std Err)
		sample size = 78	Sample size = 74	
	Baseline in hematocrit	23.8 (3.8) %	23.8 (3.3) %	
	12 week Follow up in haematocrit	33.7 (4.8) %	24.1 (3.8) %	
	HMG equivalent Mean Change*	3.3(0.33) g/dL	0.1(0.17) g/dL	3.2 (0.042) g/dL
Bennett et al, 1991 (Epoetin Beta - Hemodialysis)		sample size = 90	sample size = 41	
	Baseline	7.1 (0.1*sqrt(90)) g/dL	6.8 (0.2*sqrt(41)) g/dL	
	12 week Follow up	11.1 (0.2*sqrt(90)) g/dL	7.6 (0.3*sqrt(41)) g/dL	
	HMG Mean Change*	4.0 (0.95) g/dL	0.8(0.64) g/dL	3.2 (0.141) g/dL
Canadian et al, 1990 (Erythropoietin - hemodialysis patients)		sample size = 40	sample size = 40	
	Baseline	7.1 (0.9) g/dL	6.9 (1.0) g/dL	
	6 month follow up	10.2 (1.0) g/dL	7.4(1.2) g/dL	
	HMG Mean Change*	3.1(0.1) g/dL	0.5 (0.2) g/dL	2.6 (0.035) g/dL

*Hematocrit in % was converted to hemoglobin in g/dL by dividing by 3. Due to the information are limited from the reference, the mean change in hemoglobin and the corresponding standard deviation were derived where the baseline and follow up hemoglobin were assumed to be independent which is very conservative.

The weighted mean point estimate for mean change from baseline in hemoglobin for EPO (mean change from baseline in hemoglobin for EPO group – mean change from baseline in hemoglobin for placebo group) was estimated to be 2.859 g/dL by treating the studies as fixed effect, with a 95% confidence interval of (2.806, 2.911) and 2.993 g/dL by treating the studies as random effect, with a 95% confidence interval of (2.520, 3.466) from meta-data analysis. The lower bound of this 95% confidence interval by treating the study as random effect, 2.520 is taken to be the NI margin M_1 . To ensure that not more than 50% of the effect of EPO was lost, giving an NI margin (M_2) of 1.26.

However, a very conservative M_2 margin was chosen, 0.75, which is 29.76% of M_1 , thus ensuring preservation of 70.24% of M_1 in this study. See Figure 2 for the visual effect of NI margin based on EPO group versus placebo group in mean change from baseline in hemoglobin.

Figure 2 Active Control – Placebo differences (Point estimate, 95% CI) in History Studies

